3. OVERALL CLINICAL STUDY DESCRIPTION

This is a phase 3, multicenter, randomized, double-blind, placebo-controlled, parallel-group study with treatment of QM1114-DP in the LCL and GL, alone or in combination.

Following the informed consent and the screening process, eligible subjects will be randomly assigned to treatment in a 2:2:2:1 ratio. Subjects will receive a single treatment at baseline (Day 0) of either:

- 60 units QM1114-DP (60 units in the LCL and placebo in the GL, 118 subjects),
- 50 units QM1114-DP (50 units in the GL and placebo in the LCL, 118 subjects),
- 110 units QM1114-DP (60 units in the LCL and 50 units in the GL, 118 subjects), or
- Placebo in both the LCL and GL (59 subjects).

Randomization will be stratified by study center.

Subjects eligible for the treatment must meet the severity criteria for LCL and GL at baseline (i.e. moderate to severe LCL and GL at maximum smile and maximum frown, respectively). LCL should be bilaterally symmetrical. Baseline wrinkle severity determination will be based on both investigator and subject ratings using the 4-point photographic scale of LCL severity (LCL-ILA; LCL-SLA) and the 4-point photographic scale of GL severity (GL-ILA) and the subject 4-point categorical scale (GL-SLA).

[figure not shown]
 GALDERMA	Title 43QMI902 Clinical Study Protocol - QM1114 - LCL and GL	Doc id MA-40371
--	---	----------------------------------

Following treatment at baseline, subjects will be monitored for safety and efficacy according to the Schedule of Assessments ([Table 2](#)).

Efficacy assessments will include (Section [7.1](#)):

- Investigator 4-point Photographic Scale of LCL Severity at **CCI** maximum smile (Investigator assessment [LCL-ILA])
- Subject 4-point Photographic Scale of LCL Severity at **CCI** maximum smile (subject assessment [LCL-SLA])
- Investigator 4-point Photographic Scale of GL Severity at **CCI** maximum frown (Investigator assessment [GL-ILA])
- Subject Static 4-point Categorical Scale of GL Severity at maximum frown (subject assessment [GL-SLA])

CCI

Safety assessments will include (Section [7.2](#)):

- AEs
- Focused physical examination (FPE)
- Vital signs
- ECG
- Laboratory safety tests (chemistry and hematology)
- Production of neutralizing antibodies against QM1114-DP

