1.1.2 Number of subjects and randomization

The study will screen approximately 454 male and female adults, 18 years of age and older, with moderate to severe glabellar lines at maximum frown and moderate to severe lateral canthal lines at maximum smile in up to 15 study sites in order to enroll 413 subjects. Following the screening process, eligible subjects will be randomized at the baseline visit (Day 0) in a 2:2:2:1 ratio to:

- 60 units QM1114-DP (60 units in the LCL and placebo in the GL, 118 subjects),
- 50 units QM1114-DP (50 units in the GL and placebo in the LCL, 118 subjects),
- 110 units QM1114-DP (60 units in the LCL and 50 units in the GL, 118 subjects), or
- Placebo in both the LCL and GL (59 subjects).

Randomization will be stratified by study center.

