2.4.3 Primary analysis

The primary efficacy endpoints will be the composite responder rate based on the GL-ILA and GL-SLA of GL severity at maximum frown at Month 1 (described in [Section 1.3.3](#) and [Section 1.3.4](#), respectively) as well as the composite responder rate based on the LCL-ILA and LCL-SLA of LCL severity at maximum smile at Month 1 (described in [Section 1.3.1](#) and [Section 1.3.2](#), respectively). To evaluate the effectiveness of QM1114-DP versus placebo in the treatment of moderate to severe LCL and GL, alone or in combination, the responder rates of the QM1114-DP and placebo will be compared using the Cochran-Mantel-Haenszel (CMH) test stratified by site at the 5% significance level (2-sided). The group treated in one rhytid area alone (the QM1114-DP in LCL/placebo in GL; the placebo in LCL/QM1114-DP in GL treatment groups) and the group with concurrent LCL and GL treatment (the QM1114-DP in LCL/QM1114-DP in GL treatment group) will be analyzed separately.

The null hypothesis of no relationship between treatment and responder rate will be tested against the alternative hypothesis that there is a relationship between treatment and responder rate. For a significant result, the two-sided p-value of the comparison of the composite GL-ILA/GL-SLA and composite LCL-ILA/LCL-SLA responder rates between the QM1114-DP treated and placebo treated subjects at Month 1 using the CMH test needs to be smaller than 0.05. The Breslow-Day test will be used to assess the homogeneity of the odds ratios across all sites.

To control the type I error rate among the 4 primary efficacy comparisons, the fixed sequence procedure will be used which requires no adjustment to the level of significance. The comparisons will be done in the following order:

1. GL alone group vs placebo on the **GL scale** (i.e. the placebo in LCL/QM1114-DP in GL group vs. the placebo in LCL/placebo in GL group)
2. GL + LCL group vs placebo on the **GL scale** (i.e. the QM1114-DP in LCL/QM1114-DP in GL group vs. the placebo in LCL/placebo in GL group)
3. LCL alone group vs placebo on the **LCL scale** (i.e. the QM1114-DP in LCL/placebo in GL group vs. the placebo in LCL/placebo in GL group)
4. GL + LCL group vs placebo on the **LCL scale** (i.e. the QM1114-DP in LCL/QM1114-DP in GL group vs. the placebo in LCL/placebo in GL group)

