The estimates of the composite GL-ILA/GL-SLA and the composite LCL-ILA/LCL-SLA responder rates in each treatment group will be presented as well as the difference in responder rates (QM1114-DP responder rate – placebo responder rate). Corresponding 95% CI for the treatment group composite GL-ILA/GL-SLA and the LCL-ILA/LCL-SLA responder rates and the difference in responder rates along with the p-value for the difference will also be presented. The normal approximation (Wald) method will be used to calculate both the 95% CI for the individual treatment group composite GL-ILA/GL-SLA and LCL-ILA/LCL-SLA responder rates and the 95% CI for the difference in responder rates. The above responder rates will be presented in figures by visit and treatment group.

 GALDERMA	Title 43QMI902 Statistical Analysis Plan US - QM1114-DP - GL&LCL	Doc id MA-43265
--	---	----------------------------------

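### The 95% CI for the primary responder-rate difference leaves out the site stratification used in the randomisation and the test, so it is generally somewhat too wide when sites differ

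*SAP*

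**What the plan says.** SAP 1.1.2 states "Randomization will be stratified by study center". Protocol section 3 gives the allocation: "eligible subjects will be randomly assigned to treatment in a 2:2:2:1 ratio".

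SAP 2.4.3 then specifies three things for each of the four primary comparisons:

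- **The test.** Responder rates are "compared using the Cochran-Mantel-Haenszel (CMH) test stratified by site at the 5% significance level (2-sided"). For success, the p-value "at Month 1 using the CMH test needs to be smaller than 0.05".
- **The estimate.** Responder rates by arm "will be presented as well as the difference in responder rates", defined as the QM1114-DP rate minus the placebo rate.
- **The interval.** "The normal approximation (Wald) method will be used to calculate both the 95% CI" for the single-arm rates and for the difference. It is shown with the test result: "the difference in responder rates along with the p-value for the difference will also be presented".

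No strata, site weights or Mantel-Haenszel risk difference are named for the estimate or its interval. The sensitivity analyses in SAP 2.4.3.1 repeat the same method in other populations or with other handling of missing data. None of them adds a site-adjusted interval.

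**The concern.** The design balances the arms within center and the test uses that balance, but the reported effect size does not. The crude variance p(1-p)/n treats all subjects in an arm as one homogeneous sample. If sites differ in response, part of that variance is variation between sites, which stratified randomisation has kept out of the comparison. The difference and its interval then come from one analysis, and the p-value printed beside them from another.

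What is at stake is the precision of the effect size that will be quoted for four primary comparisons. Site differences are not far-fetched: the SAP itself plans a Breslow-Day test across sites (2.4.3) and a subgroup analysis by site (2.4.3.2).

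**Working it through.** **Inputs from the documents.** Allocation is 2:2:2:1, so 2:1 in each comparison with placebo. Enrolment is 413: 413 x 2/7 = 118 per active arm and 413 x 1/7 = 59 on placebo, which reproduces the plan's split exactly. The planned mITT is about 350, or 100 per active arm and 50 on placebo (SAP 2.7.3). There are up to 15 sites (SAP 1.1.2), expected to be of similar size (Protocol 5.1).

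**Inputs that are assumptions.** The readable text gives no expected responder rates and no between-site variation. The ranges below are assumed.

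**Step 1, formulas.** With responder rates p_t and p_c and between-site SDs of those rates s_t and s_c:

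- Crude Wald variance: p_t(1-p_t)/n_t + p_c(1-p_c)/n_c.
- Variance under site-stratified allocation: [p_t(1-p_t) - s_t²]/n_t + [p_c(1-p_c) - s_c²]/n_c.

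Example at 70%/2%, SDs 0.20/0.02, 100 against 50:

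- Crude: 0.21/100 + 0.0196/50 = 0.002492; half-width 1.96 x √0.002492 = 9.78 points.
- Stratified: (0.21 - 0.04)/100 + (0.0196 - 0.0004)/50 = 0.002084; half-width 1.96 x √0.002084 = 8.95 points.

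| Rates, active/placebo | Site SD of rates | Crude half-width (points) | Stratified half-width | Crude wider by |
|---|---|---|---|---|
| 70%/2% | 0/0 | 9.78 | 9.78 | 0% |
| 70%/2% | 0.10/0.01 | 9.78 | 9.58 | 2% |
| 70%/2% | 0.20/0.02 | 9.78 | 8.95 | 9% |
| 50%/5% | 0.10/0.03 | 11.51 | 11.31 | 2% |
| 50%/5% | 0.20/0.05 | 11.51 | 10.74 | 7% |
| 50%/30% | 0.20/0.20 | 16.04 | 14.54 | 10% |

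**Step 2, the same on the logit scale.** Simulation at about 60%/2%, with 15 sites of 7:3 or 8:4, or 8 strata of 14:7, 3,000 trials per setting. The crude interval was about 2% wider than a site-stratified one at site logit SD 0.5, and 7-8% wider at SD 1.0 (crude coverage 95.8-96.4%). Measured against the actual sampling SD at 60%/2%, the crude SE was too large by about 1.5% and about 7%.

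**Step 3, coverage and agreement with the test.** Simulation of 12 sites of 8 active and 4 placebo, 40,000 trials per scenario. The true half-width is 1.96 times the simulated SD of the crude difference. Disagreement is the share of trials in which the Wald interval and the CMH test differ on zero.

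| Rates | Site SD | Crude half-width | True half-width | Crude coverage | Disagreement |
|---|---|---|---|---|---|
| 70%/2% | 0/0 | 9.89 | 10.01 | 93.9% | 0.0% |
| 50%/5% | 0/0 | 11.64 | 11.82 | 94.3% | 0.0% |
| 50%/5% | 0.20/0.04 | 11.71 | 11.05 | 96.0% | 0.0% |
| 50%/5% | 0.25/0.04 | 11.70 | 10.67 | 96.7% | 0.0% |
| 50%/30% | 0.20/0.19 | 16.30 | 14.94 | 96.4% | 4.6% |
| 20%/5% | 0.10/0.03 | 9.98 | 9.88 | 95.2% | 8.6% |
| 15%/3% | 0.08/0.02 | 8.51 | 8.53 | 95.7% | 13.3% |

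A separate run at 60%/2% (15 sites of 7:3, 20,000 trials at each logit SD of 0, 0.5, 1.0 and 1.5) gave no disagreement in any trial.

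The direction of disagreement varies. At 50%/30% the CMH test rejects more often than the interval excludes zero (69% against 64%), which fits an interval that is too wide. At 15%/3% it is the reverse: the interval excludes zero in 78% of trials and the test rejects in 65%.

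**Step 4, which stratified variance.** At 50%/5% with SDs 0.25/0.04, the true half-width is 10.67 and the crude one 11.70. The Mantel-Haenszel difference with the Sato variance gives 11.24, and within-site variances give 10.59. At about 70%/2% with SDs 0.19/0.014 the same four figures are 9.29, 9.96, 9.82 and 9.25. When the risk difference varies by site, the Sato variance therefore keeps much of the excess. Intervals from within-site variances covered 94.2-94.8% across all scenarios run.

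**The case against.** The strongest case is that little depends on this. The CMH p-value alone decides success, the interval is descriptive, and its error is mostly on the cautious side. The crude difference is a legitimate marginal effect that matches the arm rates printed beside it. Site differences are not hidden, because the SAP tests homogeneity across sites and tabulates results by site. All of that stands. So does the remark that the SAP never calls the interval unstratified; that is inferred from a plain Wald method with no strata or weights named.

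The larger percentages also need wide site differences. With a median site at 60%, a logit SD of 0.5 puts 95% of sites between 36% and 80% responders, and an SD of 1.0 between 17% and 91%. Trained investigators and validated scales (Protocol 7.1) make the second spread hard to presume. At SD 0.5 the excess is about 2%, or roughly 0.2 points on a half-width near 10 (9.78 against 9.58).

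Three stronger readings are tempting, and none is supported:

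- A reader might infer that the interval is too wide whenever sites differ. At 15%/3% it is not: 8.51 against 8.53.
- A reader might infer that interval and test could contradict each other in the main result. With a large effect they did so in 0.0% of simulated trials.
- A reader might infer that stratifying the interval would make the two agree. At small effects or low rates, some of the disagreement arises because Wald uses the unpooled variance and CMH the null variance, and that part would remain.

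What is left is that the crude interval gives up precision the design has already secured, for no stated reason.

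**Conclusion.** The point holds as a modest loss of precision in the reported effect size. Randomisation and the primary test are stratified by site, while the difference and its 95% CI are crude. When sites differ, the interval is generally somewhat conservative: about 2% too wide at a site logit SD of 0.5 and about 7-10% at SD 1.0. There is no excess if sites respond alike or if response rates are very low. These sizes rest on assumed responder rates and site SDs, and on roughly equal sites. The primary conclusion is not at risk, since the CMH p-value alone decides it.

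**What to change.** In SAP 2.4.3, report the CMH-weighted (site-stratified) risk difference with a 95% CI built from within-stratum variances, combined over the imputed data sets by Rubin's rules. Keep the crude rates and the crude difference as descriptive columns. The test, the fixed sequence and the significance level do not change.

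Use the CMH strata, and state before unblinding that, for the interval, any stratum with fewer than 2 subjects in either arm is merged with a neighbouring one. The rule in SAP 2.1.2 does not guarantee this, because it pools only when a site has fewer than 5 subjects in total. At 2:2:2:1 a site of 7 is expected to have 7 x 1/7 = 1 placebo subject and is not pooled, and p(1-p)/(n-1) is then undefined. Even the average is thin: 350/15 = 23.3 mITT subjects per site, of whom 23.3/7 = 3.3 are on placebo.

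The cost is slightly more programming and one more rule to write down. The gain shrinks if sites are pooled into regions, since only between-region variation is then removed.

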2.4.3.1 Sensitivity analysis

To evaluate the impact of missing data on the primary endpoints, sensitivity analyses will be performed. The primary analysis specified in [Section 2.4.3](#) will be repeated using the BOCF method (detailed in [Section 2.4.2](#)), and also using the ITT OC.

In addition, a sensitivity analysis of the primary efficacy endpoints will be performed based on the PP population, and also on the Safety population to account for potential errors in randomization. The analysis method described above in [Section 2.4.3](#) will be repeated but using the PP population and Safety population.

2.4.3.2 Subgroup analysis

Additionally, to evaluate the consistency of the results of the primary analysis across different subgroups of interest, the primary analysis specified above ([Section 2.4.3](#)) will be repeated, stratifying for each of the following subgroups specified below:

- Age (less than 65 years old, 65+ years old)
- Gender (Male, Female; if enough males are recruited)
- Baseline severity score of the GL-ILA at maximum frown (Grade 2 (Moderate), Grade 3 (Severe))
- Baseline severity score of the LCL-ILA at maximum smile (Level 2 (Moderate), Level 3 (Severe, using the worst value from the right and left sides)).
- Prior botulinum toxin use (Yes, No)
- Fitzpatrick skin type (I-III, IV-VI)
- Site
- Type of Month 1 visit (Onsite, Remote)

For each subgroup, the responder rates, difference in responder rates between the treatment groups, and the corresponding 95% CI will be presented. The Breslow-Day test will be used to assess the homogeneity of the odds ratios across all the subjects within each subgroup. The subgroup analysis for type of Month 1 visit will be performed based on the ITT population.

2.4.4 Secondary analysis

To evaluate the effectiveness of a single dose of QM1114-DP in the LCL and QM1114-DP in the GL, alone or in combination, the GL-ILA at maximum frown and LCL-ILA at maximum smile responders at each visit will be presented in frequency tables. The respective responder rates (specified in [Section 1.4.2](#)) will be calculated and presented by treatment group and visit. Corresponding 95% CI for the GL-ILA at maximum frown and LCL-ILA at maximum smile responder rates will also be presented. The Clopper-Pearson (Exact) method will be used to calculate the CIs. The CMH analyses, as outlined in the Section 2.4.3, will be conducted for descriptive purposes.

The secondary analysis will be based on the ITT population with the remote visit assessments excluded. A sensitivity analysis will be conducted using the ITT population including the remote visit assessments.

The above responder rates will be presented in figures by visit and treatment group.

Effective date: 2021-02-05 13:16

Effective

Version: 1.0

 GALDERMA	<small>Title</small> 43QMI902 Statistical Analysis Plan US - QMI114-DP - GL&LCL	<small>Doc id</small> MA-43265
---	--	-----------------------------------

CCI

 GALDERMA	Title 43QMI902 Statistical Analysis Plan US - QM1114-DP - GL&LCL	Doc id MA-43265
--	---	----------------------------------

CCI

2.5 Safety analysis

All safety data will be summarized descriptively based on the safety population. All of the safety analyses will be done using OC. If deemed necessary, any analyses may be repeated using OC, BOCF, or MI as appropriate.

2.5.1 Extent of exposure

There will only be limited exposure to QM1114-DP since it is injected only once according to the treatment group assignment as described in [Section 1.1.2](#). The number of subjects receiving a single dose of QM1114-DP and placebo, respectively, will be presented.

2.5.2 Adverse events

All AE data will be summarized by treatment group. Missing dates will be imputed as described below. AEs will be summarized by SOC and PT. AEs occurring before treatment will be presented in listings only. The MedDRA version used for the coding will be noted as a footnote in the tables and listings.

A summary of all AEs will be provided, which will include:

- number (%) of subjects who did not have an AE
- number (%) of subjects with at least one TEAE and number of events
- number (%) of subjects with at least one TEAE related to study product or injection procedure
- number (%) of subjects with at least one TEAE not related to study product or injection procedure
- number (%) of subjects with at least one TEAE leading to discontinuation
- number (%) of subjects with at least one serious TEAE.

Summaries of TEAEs (including the total number of events, number and percentage of subjects) will be displayed by treatment group according to the following:

- All TEAEs by SOC and PT
- Treatment emergent SAE by SOC, PT, maximum intensity (mild, moderate, severe) and causality
- Related TEAEs by SOC and PT, and maximum intensity (mild, moderate, severe)
- Unrelated TEAEs by SOC and PT, and maximum intensity (mild, moderate, severe)
- TEAEs leading to discontinuation by SOC and PT, and maximum intensity (mild, moderate, severe)
- TEAEs by SOC, PT, and action taken (none, medical treatment, non-pharmacological treatment, subject withdrawn)

For the subject level analyses, the number and percentage of subjects who experienced at least one of the events listed above will be summarized overall and for each SOC and each PT. System organ class and PTs will be presented in descending frequency first (by the QM1114-DP in GL/QM1114-

 GALDERMA	Title 43QMI902 Statistical Analysis Plan US - QMI114-DP - GL&LCL	Doc id MA-43265
--	---	----------------------------------

Effective date: 2021-02-05 13:16

Effective

Version: 1.0

DP in LCL group), and then alphabetically if there are ties. Each subject will contribute at most one count per summarization category. In other words, if a subject has more than one TEAE with same PT, the subject will be counted only once for that PT. Similarly, if a subject has more than one TEAE for a SOC, the subject will be counted only once in that SOC and PT. For the event level analyses, the counts of each respective event will be presented. In general, percentages will be calculated using the number of subjects in the safety population for the denominator. For the subgroup analyses (described in [Section 2.5.2.1](#)) percentages will be calculated using the number of subjects in the safety population for each respective sub-category as the denominator.

For the “action taken” summary specifically, subjects will be only counted in ‘None’ category if no other action was taken. The onset/duration summaries will be presented at the event level (i.e. will include multiple AEs within the same SOC and PT). Number of days to onset and duration of event will be summarized by SOC and PT, using mean, SD, minimum, maximum, and median statistics. Time to onset will be calculated as the first day with the AE *minus* the Day 0. Duration will be calculated as the last day with the AE *minus* the first day with the AE *plus* one. The text below lists the imputation rules for partial/completely missing dates. Missing stop date will not be imputed and therefore no duration will be calculated in these cases. Instead, the number of AEs that were ongoing at the end of the study will be given.

Handling of Missing/Partial Dates

While every effort will be made to obtain full, complete information on every reported AE, the following imputation rules will be followed for any respective missing AE data:

For the purpose of calculating treatment emergence, onset time, and duration, the following date imputation rules will be used. Dates will be presented as is in the listings.

- Start Date
 - If start date is completely missing, it will be assumed that the AE started on the treatment date.
 - If the start date is missing the day, the first of the month will be used (i.e. UNK-JAN-2019 becomes 01-JAN-2019), provided the imputed date is on or after the subject’s treatment date; otherwise, the day of treatment will be used.
 - If the start date is missing the month, the month of ‘June’ will be used (i.e. 01-UNK-2019 becomes 01-JUN-2019), provided the imputed date is on or after the subject’s treatment date; otherwise, the subsequent month after treatment will be used.
 - If the start date is missing the year, the year of treatment will be used (i.e. 01-JAN-UNK becomes 01-JAN-2019), provided the imputed date is on or after the subject’s treatment date; otherwise, the subsequent year after treatment will be used.
- End Date
 - If end date is completely missing, it will be assumed that the AE is still ongoing and will not be imputed.
 - If the end date is missing the day, the last of the month will be used (i.e. UNK-JAN-2019 becomes 31-JAN-2019)
 - If the end date is missing the month, the subsequent month after the start date will be used.

 GALDERMA	Title 43QMI902 Statistical Analysis Plan US - QMI114-DP - GL&LCL	Doc id MA-43265
--	---	----------------------------------

Effective date: 2021-02-05 13:16

Effective

Version: 1.0

- If the end date is missing the year, the year of treatment will be used (i.e. 01-JAN-UNK becomes 01-JAN-2019), provided the imputed date is after the start date; otherwise, the subsequent year after start date will be used.

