In the early 1990s, patients treated with BoNT-A for blepharospasm were observed to lose their frown lines and,^{5,9} since publishing these observations, the use of BoNT-A in the aesthetic setting has accelerated. Injectable BoNT-A products have been investigated for multiple aesthetic indications in attempts to reverse the appearance of aging, especially in the facial region.² In the treatment of facial lines, the effect of BoNT-A injections usually persists for approximately 4-6 months. Facial muscle activity and severity of the facial wrinkles then returns to baseline. Full functionality of facial muscles is usually restored by approximately 6 months post-treatment.¹⁰

There are four BoNT-A products currently licensed in the United States (US) for the treatment of GL (Botox Cosmetic®, Dysport®, Xeomin® and Jeuveau™), and one licensed for the treatment of LCL (Botox Cosmetic®). QM1114-DP is a novel botulinum toxin type-A1 which is presented as a liquid formulation. Unlike the main commercially available botulinum toxins in the US, QM1114-DP is manufactured and formulated without any animal or human proteins. As a novel BoNT-A with a differentiated formulation, QM1114-DP is being developed for the treatment of moderate to severe GL and LCL in adults over 18 years.

 GALDERMA	<small>Title</small> 43QMI902 Clinical Study Protocol - QM1114 - LCL and GL	<small>Doc id</small> MA-40371
--	---	--

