7.2.6.2 Reporting Procedures

7.2.6.2.1 Procedures for Reporting Adverse Events

The collection of AEs is from the time that a subject signs the ICF to their final visit.

At each post-enrollment visit, the Investigator (or sub-Investigator) will question the subject about AEs using an open non-persuasive question to elicit reporting of AEs, for example “Have you noticed any change in your health since the last visit?” Directed questioning and examination will then be performed as appropriate.

Any AE occurring during the AE reporting period, whether it is related to the study product or not, will be recorded immediately in the source document, and described on the AE form of the eCRF along with the date of onset, severity, relationship to the study product, and outcome, without omitting any requested and known information. Additional information will be requested under certain circumstances.

 GALDERMA	Title 43QMI902 Clinical Study Protocol - QM1114 - LCL and GL	Doc id MA-40371
--	---	----------------------------------

Effective date: 2020-06-09 07:02

Effective date:

Effective

Version: 4.0

At study end, AEs assessed as related to the treatment or study procedure will be monitored until they have resolved or reached a stable condition. Other AEs will be monitored until the last visit if they have not resolved or reached a stable condition.

The Investigator will maintain all pertinent medical records in the subject's study file. If necessary and approved by the subject or their legal health care representative, the Investigator may contact the subject's personal physician or other health care provider(s) to obtain further details.

For SAEs (see Section 7.2.6.2.2) and pregnancies (see Section 7.2.6.2.3), the Sponsor is to be informed immediately by e-mail. The event must be reported by to the Safety email within 24 hours of receipt of the information (contact details in Section 7.2.6.2.2).

7.2.6.2.2 *Procedure for Reporting a Serious Adverse Event*

For a SAE occurring during the clinical study, regardless of whether it is related to the treatment or not, and of whether it is expected or not, the Investigator must do the following:

1. Take prompt and appropriate medical action, if necessary. The safety of the subject is the first priority.
2. Ensure that the event is classified as an SAE (Section 7.2.6.1.3).
3. Complete the AE form provided in the eCRF as fully as possible.

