14.3 Safety Data			
14.3.1 - 14.3.6 Exposure and Adverse Events			
14.3.1	Injection Administration and Characteristics	Safety	U
14.3.2	Overall Summary of Adverse Events	Safety	U

Table Number	Table Title	Analysis Population	(U)nique/ (R)epeat
14.3.3.1	Treatment Emergent Adverse Events by MedDRA System Organ Class and Preferred Term	Safety	U
14.3.3.2	Serious Treatment Emergent Adverse Events by Intensity, MedDRA System Organ Class and Preferred Term	Safety	U
14.3.3.3	Treatment Emergent Adverse Events Related to Study Product or Injection Procedure by Intensity, MedDRA System Organ Class and Preferred Term	Safety	R
14.3.3.4	Treatment Emergent Adverse Events That Led to Discontinuation by Intensity, MedDRA System Organ Class and Preferred Term	Safety	R
14.3.3.5	Treatment Emergent Adverse Events Unrelated to Study Product or Injection Procedure by Intensity, MedDRA System Organ Class and Preferred Term	Safety	R
14.3.3.6	Treatment Emergent Adverse Events Related to Study Product or Injection Procedure by Intensity, MedDRA System Organ Class and Preferred Term by Age	Safety	U
14.3.3.7	Treatment Emergent Adverse Events Related to Study Product or Injection Procedure by Intensity, MedDRA System Organ Class and Preferred Term by Study Site	Safety	U
14.3.3.8	Treatment Emergent Adverse Events Related to Study Product or Injection Procedure by Intensity, MedDRA System Organ Class and Preferred Term by Fitzpatrick Skin Type	Safety	U
14.3.3.9	Treatment Emergent Adverse Events Related to Study Product or Injection Procedure by Intensity, MedDRA System Organ Class and Preferred Term by Race	Safety	U
14.3.3.10	Treatment Emergent Adverse Events Related to Study Product or Injection Procedure by Intensity, MedDRA System Organ Class and Preferred Term by Gender	Safety	R
14.3.3.11	Treatment Emergent Adverse Events Related to Study Product or Injection Procedure by Intensity, MedDRA System Organ Class and Preferred Term by Prior Botulinum Toxin Use	Safety	R
14.3.4	Summary of Duration of Adverse Events Related to Study Product or Injection Procedure by System Organ Class and Preferred Term	Safety	U
14.3.5	Summary of Number of Days to Onset of Adverse Events Related to Study Product or Injection Procedure by System Organ Class and Preferred Term	Safety	R
14.3.6	Summary of Action Taken for Treatment Emergent Adverse Events Related to Study	Safety	U

2021-02-05 13:16

Effective date:

Effective

Version: 1.0

Table Number	Table Title	Analysis Population	(U)nique/ (R)epeat

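### Table 14.3.4 summarises duration only for related adverse events that have a stop date, so it may understate how long those events last

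*SAP*

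**What the plan says.** SAP 2.5.2 defines AE duration as last day minus first day plus one, and plans the summary as follows: "Number of days to onset and duration of event will be summarized by SOC and PT, using mean, SD, minimum, maximum, and median statistics". The summary is at event level, so one subject can contribute several events to the same term. The affected output is Table 14.3.4, "Summary of Duration of Adverse Events Related to Study Product or Injection Procedure by System Organ Class and Preferred Term".

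For events without an end, the SAP states "Missing stop date will not be imputed and therefore no duration will be calculated in these cases" and continues: "Instead, the number of AEs that were ongoing at the end of the study will be given". The date rules in the same section agree for a wholly absent date: "If end date is completely missing, it will be assumed that the AE is still ongoing and will not be imputed". A partial date is treated differently: "If the end date is missing the day, the last of the month will be used".

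Protocol 9.1.3.2 asks for a duration summary of all related treatment-emergent AEs. Protocol 7.2.6.2.1 says that at study end "AEs assessed as related to the treatment or study procedure will be monitored until they have resolved or reached a stable condition". Protocol 7.2.6.1.5 closes the AE reporting period at the end of the subject's participation, and 7.2.6.2.1 describes collection up to the final visit. Neither document says whether a stop date learned after exit enters Table 14.3.4.

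**The concern.** An event with no stop date is right-censored: its duration is known to be at least the time observed so far. Leaving it out discards that information. Among events with similar onset and follow-up, those left out have outlasted those kept, so the error in the mean, median and maximum runs towards shorter durations.

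How long a local effect lasts is part of its harm, and Table 14.3.4 is the planned summary of it. A reader who takes the printed maximum as the longest event seen could be wrong, because an open event may already have run longer. The plan also treats benefit and harm differently: Protocol 9.1.3 and 9.1.5 use Kaplan-Meier methods for duration of response, but no censoring-aware method is planned for duration of AEs.

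**Working it through.** The documents state no AE duration and no ongoing rate, so there is no planned figure to reproduce. The check shows the mechanism and then gives a range under stated assumptions.

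**Inputs from the documents.** A month is 28 days (Protocol Table 2), so Month 6 falls at 6 × 28 = Day 168, with a window of ±5 days. Open events get no duration (SAP 2.5.2).

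**Mechanism, with ten invented events.** Eight ended, with durations 20, 25, 30, 40, 45, 60, 75 and 90 days. Two are open after 155 and 160 days.

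- Ended only (the SAP rule): mean 385/8 = 48.1, median (40 + 45)/2 = 42.5, maximum 90.
- Counting the open events at their observed time, which is a lower bound: mean 700/10 = 70.0, median (45 + 60)/2 = 52.5, maximum at least 160.

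A count of two ongoing events beside the first line tells the reader that something is missing. It does not change 48.1, 42.5 or 90.

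**Range under assumptions.** None of these is in the documents: onset uniform over Days 0-14; durations exponential, or Weibull with shape 2; no stop date obtained after Day 168; 1,000,000 simulated events per scenario, durations rounded up to whole days. Understatement of the mean = (all-event mean − ended-only mean) / all-event mean.

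| Assumed true mean (days) | Shape | Ongoing at Day 168 | Mean: all vs ended only | Understatement | Median: all vs ended only |
|---|---|---|---|---|---|
| 14 | either | 0.0% | 14.5 vs 14.5 | 0% | no difference |
| 30 | exponential | 0.5% | 30.5 vs 29.8 | 2% | 21 vs 21 |
| 30 | Weibull | 0.0% | 30.5 vs 30.5 | 0% | 29 vs 29 |
| 60 | exponential | 6.9% | 60.5 vs 48.6 | 11.9/60.5 = 20% | 42 vs 38 |
| 60 | Weibull | 0.4% | 60.4 vs 60.0 | 0.4/60.4 = 1% | 57 vs 57 |
| 90 | exponential | 16.8% | 90.4 vs 58.1 | 32.3/90.4 = 36% | 63 vs 49 |
| 90 | Weibull | 8.3% | 90.6 vs 81.7 | 8.9/90.6 = 10% | 85 vs 80 |
| 120 | exponential | 26.2% | 120.4 vs 63.4 | 57.0/120.4 = 47% | 84 vs 56 |
| 120 | Weibull | 24.6% | 120.6 vs 92.6 | 28.0/120.6 = 23% | 113 vs 94 |

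The exponential ongoing shares can be checked in closed form. For mean m, the share is (m/14) × [exp(−154/m) − exp(−168/m)]. At m = 60: 4.286 × (0.0768 − 0.0608) = 6.8%. At m = 90: 6.429 × (0.1807 − 0.1546) = 16.7%. Both match the simulation apart from the rounding to whole days.

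Later onset makes the effect larger. With onset uniform over Days 3-30 and exponential durations with true medians of 30, 60 and 90 days, about 3%, 17% and 31% of events are open at Day 168. The ended-only medians are then about 29, 46 and 55 days.

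**The case against.** The strongest reply is that the rule turns on a missing stop date, not on being open at exit. Table 14.3.4 covers related AEs, which Protocol 7.2.6.2.1 follows after study end until resolved or stable. An event open at Month 6 that later resolves may therefore gain a stop date and a duration. This stands, and it can shrink the problem to events that are stable but unresolved, lost to follow-up, or not updated before lock. It does not remove the problem, because the documents leave open whether post-exit dates reach the table.

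A second reply is that nothing is hidden. The ongoing count is planned, all AEs and related AEs are listed with their dates (Listings 16.2.7.1 and 16.2.7.2), and suspected spread events have separate tables (14.3.7.1 and 14.3.7.2). That is fair as to disclosure. The summary statistics still rest on ended events, and SAP 2.5.2 does not say that the count appears by term and arm next to each duration.

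Third, a stop date missing only its day is moved to the end of the month, which lengthens some durations. This is true, but it applies to partial dates and gives nothing to open events.

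A reader might infer more than the documents support:

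- *That the longest toxin effects certainly drop out.* There is no bias if every related AE has a stop date, and a late-onset open event may have been observed only briefly.
- *That an event judged stable never receives a stop date.* No passage says how the end of such an event is recorded.
- *That AEs last as long as the treatment effect.* Protocol 1.1 says "Full functionality of facial muscles is usually restored by approximately 6 months post-treatment", and puts the effect on facial lines at about 4-6 months. These statements describe treatment effect and muscle recovery, not the duration of any AE.
- *That the rule makes the arms look alike.* This presumes that AE duration differs between arms, which nothing in the documents shows. The safety analysis is descriptive.

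**Conclusion.** The point holds as a limited one. Table 14.3.4 summarises right-censored durations on completed cases, so it may understate the duration of related AEs, and its maximum can be exceeded by an event still open. The direction is clear wherever a related AE lacks a stop date.

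The size cannot be derived from the documents. It is nil for short events or with complete stop dates, about 1-20% of the mean at an assumed true mean of 60 days, and about 10-36% at 90 days. Those ranges depend on the assumed shapes and onset, and on no stop date being obtained after Day 168, so post-study follow-up would reduce them. No efficacy result or hypothesis test is affected. This is an inexpensive improvement to one descriptive safety table.

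**What to change.** In SAP 2.5.2 and Table 14.3.4:

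1. State that stop dates recorded before database lock are used, including those from post-study follow-up under Protocol 7.2.6.2.1.
2. Treat related AEs still without a stop date as censored at the last recorded contact, which is study exit if no later contact is recorded.
3. Show the number ongoing beside each system organ class and preferred term, by arm.
4. Report the maximum including censored times, marked with a plus sign.
5. Give a Kaplan-Meier median where there are enough events. Because the summary is at event level, use the first event per subject and preferred term, or a confidence interval that allows for several events per subject. For sparse terms, list the individual durations with the plus sign; at 118, 118, 118 and 59 subjects per arm many terms may be sparse.
6. Limit the sentence on missing stop dates to dates that are wholly missing, since partial end dates are imputed in the same section.

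The cost is SAP wording, a little programming for one table, and a slightly less favourable duration figure. No clinical procedure or follow-up rule changes. Post-exit contact dates can be used only where they are captured, which the documents do not confirm.
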